7.0 EVALUATIONS/MATERIAL AND DATA TO BE ACCESSIONED

Timing of protocol therapy administration, response assessment studies, and surgical interventions are based on schedules derived from the experimental design or on established standards of care. Minor unavoidable departures (up to 72 hours) from protocol directed therapy and/or disease evaluations (and up to 1 week for surgery) for valid clinical, patient and family logistical, or facility, procedure and/or anesthesia scheduling issues are acceptable per COG administrative Policy 5.14 (except where explicitly prohibited within the protocol).

7.1 Required Clinical, Laboratory and Disease Evaluations

All baseline studies must be performed prior to starting protocol therapy unless otherwise indicated below. **Obtain other studies prior to start of subsequent cycles and as otherwise indicated.**

STUDIES TO BE OBTAINED	Baseline	Prior to Each Cycle	During Each Cycle	When Patient is Removed from Protocol Therapy
History	X	X		
Physical Exam (Ht, Wt, VS)	X	X		X
Performance Status	X	X		X
CBC (differential, platelets)	X	X	Weekly ^A	X
Urinalysis	X	X		X
Electrolytes (including BUN, Calcium, PO ₄ , Magnesium)	X	X	Weekly	X
Creatinine	X	X		
Total protein, AST, ALT, albumin, bilirubin	X	X		X
Pregnancy test (serum or urine, with sensitivity of 25 mIU/mL) (for females of childbearing potential)	X ^B	X ^B	Weekly ^C	X ^D
Confirmation of use of 2 effective methods of birth control OR confirmation of complete abstinence (for female patients of childbearing potential)	X	X		
Education and Counseling (all patients) ^E		X		X
Brain MRI with and without gadolinium	X ^F	X ^G		X
Spine MRI with and without gadolinium ^{F,H}	X	X ^G		X
Pharmacokinetic studies (see Section 13.0)			X ^I	

^A If patient develops hematologic toxicity as defined in [Section 5.2](#), CBCs should be checked every 3 to 4 days until recovery.

^B Obtain 2 weeks prior to study enrollment and again within 24 hours prior to Day 1 of each cycle.

^C Obtain weekly during cycle 1. Females with irregular menstruation must have a pregnancy test every 14 days while receiving protocol therapy (including breaks in treatment). Pregnancy test is also required if patient misses her period or has unusual menstrual bleeding.

^D Pregnancy testing must also occur at Day 28 (and at Day 14 if female has irregular menstruation) after lenalidomide discontinuation.

^E The Lenalidomide Education and Counseling Document ([Appendix III](#)) must be completed and signed by a trained counselor at the site prior to each dispensing of lenalidomide.

^F Obtain brain MRI within 1 week prior to study enrollment. Spine MRI (if necessary) may be obtained within 2 weeks prior to enrollment.

^G Obtain prior to each odd-numbered cycle of therapy (ie, prior to cycles 3, 5, 7, 9, 11 and 13) for the first 13 cycles. During cycles 14-26, imaging will be performed every third cycle (ie, prior to

16, 19, 22 and 25), after cycle 26, and as clinically indicated. See [Section 14.0](#) for imaging requirements.

^h Obtain in patients with a history of spinal or leptomeningeal disease, or those patients with symptoms suspicious of spinal disease. Obtain spine MRI at same time points as brain MRI.

ⁱ PK blood sample must be obtained prior to the daily dose between Day 5-21 of cycle 1 at the time of routine safety lab monitoring. In the event of a dose reduction, a blood sample must also be obtained between Day 5-21 of the cycle following the dose reduction.

This table only includes evaluations necessary to answer the primary and secondary aims. Obtain other studies as indicated for good clinical care.

7.2 Follow-up

See COG Late Effects Guidelines for recommended post treatment follow-up:
<http://www.survivorshipguidelines.org/>

Note: Follow-up data are expected to be submitted per the Case Report Forms (CRFs) schedule. This includes required pregnancy testing for all female patients of childbearing potential on Day 28 following the last dose of lenalidomide. Patients with irregular menstrual cycles must have pregnancy testing completed on Day 14 and Day 28 following the last dose of lenalidomide.

8.0 CRITERIA FOR REMOVAL FROM PROTOCOL THERAPY AND OFF STUDY CRITERIA

8.1 Criteria for Removal from Protocol Therapy

- a) Progressive disease (see definition in [Section 10.0](#)).
- b) Significant toxicity at least possibly attributed to lenalidomide despite two dose reductions (as stated in [Section 5.0](#)).
- c) Refusal of further protocol therapy by patient/parent/guardian.
- d) Completion of 26 cycles of protocol therapy.
- e) Physician determines it is in patient's best interest.
- f) Development of a second malignancy.
- g) Patient becomes pregnant while on study.
- h) Refusal to cooperate with required birth control methods or to commit to complete abstinence.
- i) Development of a thromboembolism, unrelated to central line.
- j) Evidence of toxic epidermal necrolysis (TEN) or Stevens-Johnson syndrome.

Patients who are off protocol therapy are to be followed until they meet the criteria for Off Study (see below). Follow-up data will be required unless consent was withdrawn.

8.2 Off Study Criteria

- a) Death.
- b) Lost to follow-up.
- c) Patient enrollment onto another COG study with tumor therapeutic intent.

- d) Withdrawal of consent for any further data submission.
- e) The fifth anniversary of the date the patient was enrolled on this study.

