3.0 STUDY ENROLLMENT PROCEDURES AND PATIENT ELIGIBILITY

3.1 Study Enrollment

3.1.1 Patient Registration

Prior to enrollment on this study, patients must be assigned a COG patient ID number. This number is obtained via the eRDE system once authorization for the release of protected health information (PHI) has been obtained. The COG patient ID number is used to identify the patient in all future interactions with COG. If you have problems with the registration, please refer to the online help.

A Biopathology Center (BPC) number will be assigned as part of the registration process. Each patient will be assigned only one BPC number per COG Patient ID. For additional information about the labeling of specimens please refer to the Pathology and/or Biology Guidelines in this protocol.

Please see [Appendix X](#) for detailed CTEP Registration Procedures for Investigators and Associates, and CTSU Registration Procedures including: how to download site registration documents; requirements for site registration, submission of regulatory documents and how to check your site's registration status.

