9.3.1.2 Secondary Endpoints

- Time to treatment failure (Event-free survival, EFS) – the time from study enrollment to tumor progression, tumor recurrence, death from any cause, or occurrence of a second malignant neoplasm.

- Time to death (Overall survival, OS) – the time from study enrollment to death from any cause.

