Disease progression will be based on the results of institutional review. Standard survival methods will be used for analysis of EFS and OS. Analyses include log rank tests and the product-limit (Kaplan-Meier) estimate for estimation of EFS and OS probability. Comparison of EFS between the two dose levels will primarily be exploratory. With 74 patients, we will have only approximately 69% power to detect a 15% increase in long-term EFS (30% to 45%) with 50% patients receiving high dose vs. 50% receiving low dose, based on a one-sided logrank test with 20% Type I error rate.

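### Survival follow-up stops when a patient joins another COG treatment study, so Kaplan-Meier overall survival is likely, but not certain, to be overstated by an unknown amount

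*Combined protocol and SAP*

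**What the plan says.** Section 8.1 follows patients who have stopped protocol therapy only until one of the off-study criteria in 8.2 is met. Besides death, loss to follow-up and withdrawal of consent, 8.2 lists as criterion (c) "Patient enrollment onto another COG study with tumor therapeutic intent", and as the outer limit (e) "The fifth anniversary of the date the patient was enrolled on this study".

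Section 9.3.1.2 lists OS as a secondary endpoint, defined as "the time from study enrollment to death from any cause". Section 9.4 adds: "Standard survival methods will be used for analysis of EFS and OS", naming the product-limit estimate and log-rank tests. Section 9.11 also tests the risk of death by number of prior regimens with a stratified one-sided log-rank test.

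No section gives an OS censoring rule, a provision for survival follow-up after 8.2(c), or a sensitivity analysis. Section 7.2 refers to the case report form schedule, which is not part of these documents.

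Section 3.1.1 does provide a possible link: "The COG patient ID number is used to identify the patient in all future interactions with COG".

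**The concern.** Kaplan-Meier and log-rank methods assume that a patient censored at a given time has the same later risk as those still followed. Criterion (c) is unlikely to meet that assumption. Section 4.2.1 bars other cancer therapy on study, so entry to another treatment study comes after lenalidomide stops, and progression is the first reason in 8.1 for stopping. Section 9.1 shows the same route into this trial: it expects about half of the children on an earlier COG study to progress and become eligible here.

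If progressed patients leave the risk set, those who remain are increasingly patients without progression, and the curve is carried by their lower risk. At stake is the reported level of OS. OS comparisons would also be affected if leaving, or the risk after leaving, differed between the groups compared.

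**Working it through.** **The plan's own figure.** The documents state no OS figure. The nearest is the EFS power in 9.4: about 69% for 30% vs 45%, 74 patients, one-sided 20%.
- Hazard ratio = ln 0.45 / ln 0.30 = 0.663.
- Expected events = 74 × (0.70 + 0.55)/2 = 46.25.
- Schoenfeld power = Φ(0.5 × √46.25 × 0.4106 − 0.8416) = Φ(0.555) = 71%.
- Two proportions with 37 per arm: Φ((0.15 − 0.8416 × 0.1126)/0.1112) = Φ(0.497) = 69%.

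The stated figure reproduces and is not in dispute. The same EFS values imply that 55-70% of patients have an event, which is 41 to 52 of 74.

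**Size of the OS error.** Every input here is an assumption:
- 60% of patients progress, at exponential times with mean 1.5 years (rate g = 0.667 per year); the other 40% neither progress nor die within 5 years.
- After progression the death rate is λ = 0.05 or 0.10 per year.
- A share s = 10%, 30% or 50% of progressors join another COG study, on average 3 months after progression.
- From then on, joiners die at r × λ.

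*True 5-year OS when r = 1* is 0.40 + 0.60 × (g·e^(−5λ) − λ·e^(−5g))/(g − λ).
- λ = 0.05: 0.40 + 0.60 × (0.5192 − 0.0018)/0.6167 = 90.3%.
- λ = 0.10: 0.40 + 0.60 × (0.4044 − 0.0036)/0.5667 = 82.4%.

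*Kaplan-Meier under 8.2(c)* tends to exp(−∫ λ·P(t)/A(t) dt) over 0 to 5 years. P(t) is the fraction who have progressed and are still followed, and A(t) is the fraction still followed at all. With r = 1 and s = 30% to 50%, 90.3% is read as 91.9% to 93.3%, and 82.4% as 85.3% to 87.8%.

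Kaplan-Meier minus true 5-year OS, in percentage points:

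| Joiners' hazard (r) | λ | s = 10% | s = 30% | s = 50% |
|---|---|---|---|---|
| same (1) | 0.05 | +0.48 | +1.58 | +2.96 |
| same (1) | 0.10 | +0.86 | +2.87 | +5.36 |
| half (0.5) | 0.05 | +0.05 | +0.30 | +0.83 |
| half (0.5) | 0.10 | +0.13 | +0.67 | +1.70 |
| quarter (0.25) | 0.05 | −0.18 | −0.38 | −0.32 |
| quarter (0.25) | 0.10 | −0.29 | −0.59 | −0.41 |
| twice (2) | 0.05 | +1.22 | +3.80 | +6.66 |
| twice (2) | 0.10 | +1.97 | +6.20 | +10.91 |

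**Where the sign changes.** At any time, the estimate is pushed up when r exceeds P(t)/A(t), the proportion of still-followed patients who have progressed. Interpolating between the quarter and half rows puts break-even at r = 0.25 + 0.25 × 0.18/0.23 = 0.45 (λ = 0.05, s = 10%) and at r = 0.25 + 0.25 × 0.41/2.11 = 0.30 (λ = 0.10, s = 50%).

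**A second set of assumptions gives a similar picture.** It takes 5-year EFS of 30% or 45%, 5-year survival after progression of 60-90%, and 10-50% joining. The error is +0.2 to +4.9 points at the same hazard, about 0 to +1.6 at half, −0.9 to 0 at a quarter, and +0.4 to +10.7 at twice.

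**Against sampling error.** With 74 patients and complete follow-up, the standard error of 5-year OS is √(0.90 × 0.10/74) = 3.5 points at 90% and √(0.825 × 0.175/74) = 4.4 points at 82.5%.

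**The case against.** **Frequency and reason are unknown.** The documents do not say how many patients join another COG study, or why. Section 8.1 lists nine reasons other than progression for stopping therapy, including toxicity, refusal and completing 26 cycles. Criterion (c) is also narrow: a non-COG trial, or treatment outside any trial, does not end follow-up, and the paediatric phase I study in CNS tumours described in 2.4 was run by another consortium. This stands. A reader might infer that exit mostly follows progression, but that is inference. The accrual reasoning in 9.1 shows eligibility for a next study, not uptake. At 10% joining with equal hazard, the error is under 1 point.

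**The direction is not assured.** Patients fit enough for a new study may be at lower risk. This stands in part. The joiners' hazard would have to fall to roughly 0.30-0.45 of that of other progressors before the error vanished, which is possible.

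**Log-rank tests are not shifted because the OS level is.** This stands. If exit and later risk are alike in the groups compared, the null comparison is not biased. The documents give no evidence of a difference, either by dose or by number of prior regimens.

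**OS carries little weight.** It is absent from the objectives in 1.1 and 1.2 and has no target or power. The 9.5 decision uses response and 6-month progression. EFS counts progression as an event, so an exit after progression does not alter it. All of this stands and limits the consequence.

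**Follow-up might continue anyway.** The last sentence of 8.1 requires follow-up data unless consent is withdrawn. Read alone, it could cover patients under (c), but the sentence before it sets off-study status as the end point, and nothing in 8.2 exempts survival.

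**Conclusion.** The point holds as a likely but unquantified error in the level of OS. Followed as written, the plan censors OS at an event plausibly tied to prognosis and collects nothing afterwards to correct it.

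Under the assumptions in the first table, 5-year OS is misread by about +0.5 to +5 points at equal hazard, 0 to +2 at half, slightly below zero at one quarter, and up to about +11 at twice. Most of the equal-hazard values lie below one standard error of the estimate. Unlike sampling error, though, this error would not shrink with more patients.

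A reader might go further and say that OS will be overstated, or that the OS log-rank tests are biased in favour of treatment or of one dose. The documents do not support either statement. They give no rate of joining, no death rate after progression and no sign of differential exit. The primary response endpoint and the 9.5 rule are unaffected, as is EFS when progression comes first. This is a worthwhile improvement to a secondary endpoint, not a threat to the trial's main conclusion.

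**What to change.** In 8.2, keep (c) as the end of treatment and tumour data submission, but continue vital status and date of death to the existing fifth-anniversary limit, subject to consent. These could come from the later COG study's records through the common COG patient ID. In 9.3.1.2 or 9.4, state the OS censoring rule. Report the number of patients who enter another COG study by regimen and, for the 9.11 test, by prior-regimen group. If some deaths cannot be retrieved, add a sensitivity analysis that varies the joiners' hazard as in the table.

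The cost is a change of wording and a small data linkage between COG studies, with no added visits expected. Section 3.1.1 describes the ID but no survival linkage, and the consent pages are not in the documents reviewed, so feasibility and consent coverage must be confirmed first.

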9.0 STATISTICAL CONSIDERATIONS

9.1 Sample Size and Study Duration

Approximately 45 patients per year less than 10 years of age with progressive/recurrent and high-risk LGA were enrolled on COG-A9952, *Chemotherapy for Progressive Low Grade Astrocytoma in Children Less Than Ten Years Old*. About half of these children (22 patients) would be expected to progress and would be eligible for the current study.

The total accrual of newly diagnosed LGA patients on CCG-9891/POG-9130, *Treatment of Newly Diagnosed Low Grade Astrocytomas*, was 713 over a period of 5 years. About 40% of these patients were older than 10 years of age and 20% progressed within 6 years of diagnosis. This corresponds to about 11 patients per year older than 10 years with progressive LGA. Adding to this those who will be entered because of symptomatic, incomplete resections, we would expect approximately 20 patients per year older than 10 years of age.

Adding together patients who are younger than and those older than 10 years of age (22 + 20 = 42), and taking into account patients who may opt for other treatments and the eligibility criteria of at least 1 prior therapy including carboplatin, we expect a total of 30 patients with recurrent or progressive low-grade glioma per year.

This study will enroll only patients with pilocytic astrocytoma and progressive optic pathway gliomas. Based on prior COG enrollment, we estimate 70% of low grade glioma patients to be in this subset (30*0.7=21/yr). The total accrual target for this study is 74 patients enrolled in 3.5 years. Considering that some patients enrolled may be found to be ineligible, the maximum number of patients expected to be accrued is 80 patients.

9.2 Study Design

This is a randomized study to estimate the response rate of children with recurrent or progressive pilocytic astrocytoma and optic pathway gliomas who are treated with lenalidomide assigned to either Regimen A low dose (20 mg/m²/dose) or Regimen B high dose (115 mg/m²/dose).

9.3 Methods of Analysis

9.3.1 Endpoints

9.3.1.1 Primary Endpoint

- Objective response – best response determined from the sequence of the objective statuses described in [Section 10.0](#) ‘Response Criteria.’

9.3.1.2 Secondary Endpoints

- Time to treatment failure (Event-free survival, EFS) – the time from study enrollment to tumor progression, tumor recurrence, death from any cause, or occurrence of a second malignant neoplasm.

- Time to death (Overall survival, OS) – the time from study enrollment to death from any cause.

9.4 Analysis of Efficacy

A total of 74 eligible patients will be enrolled on this trial. Patients will be randomly assigned to either the low dose (Regimen A) or the high dose arm (Regimen B). Each patient will be classified according to their 'best response' for the purposes of analysis of treatment effect. Best response is determined from the sequence of the objective statuses described in [Section 10.0](#) 'Response Criteria.' A responder is defined as a patient who achieves a best overall response of CR or PR at any time on the study. If a patient achieves a PR or CR and later has progressive disease or relapse, then the patient will be counted as a responder. The response rate will be calculated as the ratio of the number of patients who demonstrate response (CR or PR) divided by the number of patients evaluable for response. The 95% confidence bounds for response rate are shown in the table below for several different outcomes. The computation is based on the binomial distribution, assuming the availability of 30 evaluable patients (7 inevaluable patients) for response in each arm (each dose level). All patients eligible for study who receive any study drug will be considered evaluable for response. Any patient who goes off protocol therapy for any reason (patient/parent/physician choice, adverse event profile, etc.) prior to the first response evaluation will be considered a non-responder. For example, an observed response rate of 33% (10/30) will be consistent with the view that 17% or more patients will respond to the treatment.

Outcome (#Response/#Patients)	95% Exact Confidence Bound on Response Rate
20/30	(0.47, 0.83)
15/30	(0.31, 0.69)
10/30	(0.17, 0.53)
5/30	(0.06, 0.35)

There would be modest power to compare the response rates for the 2 dose cohorts. With 74 patients, we would have 80% power to detect a response rate difference of 35% vs. 15%, at the 1-sided 20% significance level.

Disease progression will be based on the results of institutional review. Standard survival methods will be used for analysis of EFS and OS. Analyses include log rank tests and the product-limit (Kaplan-Meier) estimate for estimation of EFS and OS probability. Comparison of EFS between the two dose levels will primarily be exploratory. With 74 patients, we will have only approximately 69% power to detect a 15% increase in long-term EFS (30% to 45%) with 50% patients receiving high dose vs. 50% receiving low dose, based on a one-sided logrank test with 20% Type I error rate.

9.5 Monitoring for Efficacy

Patients will be randomly assigned to either the low dose or the high dose treatment. Of the 37 patients on each treatment, we will closely monitor the first 20 patients enrolled. For each regimen, the early stopping criterion and the decision regarding ultimate further interest in this agent will be based on the number of objective responses and disease progressions in the first 6 months of treatment. If the early stopping rule is met for one treatment, that particular arm will be closed and the other arm will continue as planned.

A true response rate of 5% and a true early (6-month) progression rate of 40% are considered inadequate, whereas a true response rate of 20% and a true early (6-month) progression rate of 25% would be sufficient for further interest in this agent.

The study will be a 2-stage design, with 20 evaluable patients in the first stage and 17 evaluable patients in the second stage (37 patients total per treatment regimen), with decisions made as follows:

Number of Evaluable Patients Enrolled	Results	Decision
Stage I: 20 evaluable patients	Zero or one responders or 10 or more with early progression	Terminate enrollment with the conclusion the regimen does not demonstrate sufficient disease control
	All other configurations of response or early progression	Continue to the next stage and enroll 17 more patients
Stage II: 17 additional evaluable patients (Total of 37: 20 from Stage I and 17 from Stage II)	Cumulatively 3 or fewer responders or 15 or more with early progression	Conclude the regimen does not demonstrate sufficient disease control
	All other configurations of response or early progression	Conclude the regimen demonstrates sufficient disease control for further investigation

A summary of the operating characteristics of this design are provided below:

Response Probability	Early Progression Probability	Probability of Stopping at First Stage	Probability Accept Regimen
0.05	0.40	0.78	0.05
0.10	0.40	0.51	0.24
0.20	0.30	0.11	0.81
0.15	0.25	0.18	0.73
0.20	0.25	0.08	0.88

9.6 Monitoring for Toxicity

“Toxic events” will be defined as one in which a patient has two dose reductions and then experiences another significant toxicity as defined in [Section 5.0](#), irrespective of attribution. A two-stage stopping rule will be used to monitor for an excessive number of these toxic events. All patients described below must be evaluable for toxicity. All patients who receive at least one dose of lenalidomide will be evaluable for toxicity. A review of treatment feasibility and patient safety will be undertaken if we observe at least 5/18 or 8/36 toxic events. The rule will be met about 4% of the time if the true incidence of toxic event is 10%, and 90% of the time if the true incidence is 30%.

